10. ANNEXES

As the SAP and TFL TOC has been developed using the old template and process, we will not have TFL as annex to this SAP. All the template applicable to the study has been added in the SAP in Section 13.

10.1. Business rules for standard data derivations and statistical methods

10.1.1. Attributing events to vaccine doses

The dose relative to an event is the most recent study dose given to a subject prior to the start of a given event. For example, if the start date of an adverse event is between Dose 1 and Dose 2, the relative dose will be Dose 1.

If an event starts on the same day as a study dose, the relative dose will be derived from the additional information provided in the CRF using the contents of the flag indicating if the event occurred before or after vaccination. If 'after vaccination' is selected, the relative dose for the event will be the one administered on the start day of the event. If 'before vaccination' is selected, the relative dose for the event will be the dose prior to this one.

10.1.2. Handling of missing data

10.1.2.1. Dates

When partially completed dates (i.e. with missing day or month) are used in calculations, the following standard rules will be applied:

- A missing day will be replaced by 15
- A missing day and month will be replaced by June 30th.

The following exceptions apply:

- Adverse event start dates with missing day:
 - If the event starts in the same month as at least one of the study doses, the contents of AE.AESTRTPT (the flag indicating if the event occurred before or after vaccination) will be used to complete the date. If 'after vaccination' is selected, the imputed start date will match the first (or only) study dose given during that month. If 'before vaccination' is selected, the imputed date will be one day before the first (or only) study dose given during that month.
- Adverse event start dates with missing day and month:
 - If the event starts in the same year as at least one of the study doses, the contents of AE.AESTRTPT (the flag indicating if the event occurred before or after vaccination) will be used to complete the date. If 'after vaccination' is selected, the imputed start date will match the first (or only) study dose given during that

year. If ‘before vaccination’ is selected, the imputed date will be one day before the first (or only) study dose given during that year.

All other cases of incomplete AE or concomitant medication/vaccination start date will follow the standard rules above.

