5.3.2.4. Unsolicited Adverse Events

All the unsolicited adverse events occurring during the study, judged either as related, or not related to vaccination by the investigator, will be recorded. All the unsolicited adverse events/AE of specific interest (Spontaneous or excessive bleeding) occurring during the 30-day (Day 1 to Day 30) follow up period after each vaccination, and all serious adverse events/AE of specific interest (RSV LRTI) occurring from Dose 1 up to study end will be recorded according to the protocol-specified reporting rules. The original verbatim terms used by investigators to identify adverse events in the CRFs will be mapped to preferred terms using the MedDRA dictionary. The unsolicited adverse events will then be grouped by MedDRA preferred terms into frequency tables according to system organ class. Adverse events judged by the investigator as at least possibly related to study vaccine will be summarized by vaccine group, according to system organ class and preferred term within system organ class. When an unsolicited adverse event occurs more than once for a subject, the maximal severity and strongest relationship to the vaccine group will be counted.

Only vaccine-emergent adverse events will be analyzed, i.e., excluding those after a subject has given informed consent but before vaccination. The selection of unsolicited adverse events and the assignment to time intervals will be done by day of onset and not by days ongoing/persisting.

The analysis of unsolicited adverse events during the 30-day post vaccination period includes the following categories:

- Any unsolicited adverse event.
- Possibly related unsolicited adverse events.
- Grade 3 unsolicited adverse events
- Grade 3 related unsolicited adverse events.
- Serious adverse events (SAEs)
- Possibly related SAEs.
- Medically attended adverse events
- AE of specific interest (spontaneous or excessive bleeding)

SAE and AE of specific interest (RSV-LRTI) has to be reported from Day 1 up to Day 61, from Day 1 to end of 1st RSV season and from Day 1 to end of 2nd RSV season.

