9.2. RTI and LRTI

During the analysis of the study, all cases identified during the surveillance of RSV-RTI will be definitively classified as either RTI, LRTI, severe LRTI or very severe LRTI according to the standardized case definitions (Table 6 in the SAP) based on the available World Health Organization (WHO) case definitions (Table 6 in the protocol)

Table 6 Case definitions for data analysis

Case	At sea level up to 2500 meters elevation	Above 2500 meters elevation
RSV-RTI	Runny nose OR blocked nose OR cough AND Confirmed RSV infection ⁴	Same
RSV-LRTI	History of cough OR difficulty breathing ¹ AND SpO ₂ < 95% ² , OR RR increase ³ AND Confirmed RSV infection ⁴	Same but with SpO₂ < 92%
severe RSV-LRTI	Meeting the case definition of RSV-LRTI AND SpO ₂ < 93% ² , OR lower chest wall in-drawing	Same but with SpO₂ < 90%
very severe RSV-LRTI	Meeting the case definition of RSV-LRTI AND SpO ₂ < 90% ² , OR inability to feed, OR failure to respond / unconscious	Same but with SpO₂ < 88%

Case	At sea level up to 2500 meters elevation	Above 2500 meters elevation
RSV hospitalization	Confirmed RSV infection ⁵ AND Hospitalized for acute medical condition ⁶	Same
All-cause LRTI	History of cough OR difficulty breathing ¹ AND SpO ₂ < 95% ² , OR RR increase ³	Same but with SpO₂ <92%

LRTI = lower respiratory tract infections; RR = respiratory rate; RTI = respiratory tract infections; SpO₂ = blood oxygen saturation.

¹ Based on history reported by parents.

² The lowest value during the course of illness will be used.

³ RR increase defined as:≥ 50/minute (2 to 11 months of age) ; ≥ 40/minute (12 months of age or above) ;
The highest value during the course of the illness will be used.

⁴ RSV infection confirmed on nasal swab positive for RSV A or B by quantitative Reverse Transcription Polymerase Chain Reaction (qRT-PCR).

⁵ RSV sampling and testing is based on medical judgment of medical practitioner or driven by algorithm.

⁶ Hospitalization is defined as a medical decision that the infant requires admission for observation or treatment.

- For the analysis of RTI episode, a new RTI episode will be defined as any occurrence of cough, runny nose, blocked nose, wheezing or difficulty breathing with an interval of at least 7 symptom free days since the last episode of RTI that was diagnosed.
- For molecular biology (qRT-PCR test), the following cut-off will be applied: -

System	Component	Method	Unit	Cut-off

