10.1.3.11. Duration of events

The duration of an event with a start and end date will be the number of days between the start and end dates plus one day, i.e. an event that starts on 03MAR2018 and ends on 12MAR2018 has a duration of 10 days.

The duration of solicited events will be calculated as the sum of the individual days with the symptom reported at grade 1 or higher.

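### Partial dates are imputed without checking the event's other recorded date, so events can start after they end and, mainly after Dose 2 in Placebo countries, leave the 30-day window

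*SAP*

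**What the plan says.** - **Scope (SAP 10.1.2.1).** The rule is general: "When partially completed dates (i.e. with missing day or month) are used in calculations, the following standard rules will be applied". It therefore reaches end dates and, on its wording, RTI dates.
- **Defaults (10.1.2.1).** "A missing day will be replaced by 15", and "A missing day and month will be replaced by June 30th".
- **Exceptions (10.1.2.1).** These cover AE start dates only, in a month or year that holds a study dose. If the before/after flag says after, "the imputed start date will match the first (or only) study dose given during that month" (or that year). If it says before, the start is the day before that dose. Otherwise, "All other cases of incomplete AE or concomitant medication/vaccination start date will follow the standard rules above".
- **Windows (5.3.2.4).** For unsolicited AEs, "assignment to time intervals will be done by day of onset and not by days ongoing/persisting".
- **Duration (10.1.3.11).** For an event with a start and an end date, it "will be the number of days between the start and end dates plus one day".
- **RTI episodes (9.2).** A new episode is one "with an interval of at least 7 symptom free days since the last episode of RTI that was diagnosed". The section gives no rule for partial dates.

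Neither the defaults nor the exceptions refer to the event's other recorded date, and no other section of the SAP adds such a limit.

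**The concern.** A missing day does not mean that nothing is known. A recorded end date limits when the event can have started, and a recorded start limits when it can have ended. A rule that ignores this can produce dates that contradict data already in the database.

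Two outputs are exposed. The SAE, LRTI and bleeding listings (Templates 23 to 25) carry a duration column, which would show negative values. More importantly, unsolicited AEs and bleeding episodes within 30 days of each vaccination are primary endpoints (section 3.2.1) and are placed by onset date alone, so a wrong imputed start can remove an event that the recorded dates put inside the window. RTI episode counts could also be affected if symptom dates are partial.

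**Working it through.** The SAP gives no figure to reproduce here. The check applies its rules to worked dates and then enumerates.

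**Inputs.** The rules above; onset day 1 is the day of vaccination (10.1.3.10); the window is Days 1-30 (3.2.1); Placebo countries have no injection after Visit 3 and all other countries have one at Visit 5 (Table 1); the allowed Visit 3 to Visit 5 interval for the per-protocol set is 28-37 days (Table 4).

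**Impossible order.** Duration = end - start + 1.

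| Recorded | Imputed | Duration |
|---|---|---|
| Start 20 March, end March | End 15 March | 15 - 20 + 1 = -4 |
| Start 20 October, end year only (same year) | End 30 June | -112 + 1 = -111 |
| Start April (no dose that month), end 5 April | Start 15 April | 5 - 15 + 1 = -9 |
| Start February, flag before, dose 20 February, end 8 February | Start 19 February | 8 - 19 + 1 = -10 |

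The last row shows that the dose-based exception has the same gap. For 5-day events spread evenly over a year, the imputed end precedes the start in 137/365 = 37.5% when the end day is missing. Under the default rule, the imputed start follows the end in 120/365 = 32.9% when the start day is missing.

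**Leaving the window.** Placebo country, Dose 2 on 10 March: Day 30 is 8 April. An AE starting in April and ending on 5 April began between 1 April (Day 23) and 5 April (Day 27). The rule gives 15 April, Day 37.

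**How often, given a missing start day.** I took 365 Dose 1 dates with doses at Days 1 and 31 (and 61 where given), each of onset Days 1-30 (365 x 30 = 10,950 cases per dose), and a correct flag.

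- After Dose 1, any country: 0% leave the window.
- After Dose 2 with a Visit 5 injection: 0% leave, because the exceptions apply.
- After Dose 2 in Placebo countries: 5,219/10,950 = 47.7% of onsets fall in a month without a dose. Of all onsets, 1,260/10,950 = 11.5% leave; of those in a month without a dose, 1,260/5,219 = 24.1% leave.

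Off-nominal visits can produce the error elsewhere. With Dose 2 on 10 January and the next injection on 16 February (37 days later), a true onset on 3 February (Day 25) flagged before becomes 15 February, Day 37.

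**The reverse error.** Placebo country, Dose 2 on 25 January, true onset 26 February (Day 33): the imputed 15 February is Day 22, so a late event is moved in.

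**RTI episodes.** Symptoms ending on 20 December with the day missing, next symptoms on 24 December: the true gap is 3 symptom-free days (21-23), the imputed gap is 8 (16-23), so one episode becomes two. Ending on 5 December, next symptoms on 18 December: the true gap is 12 (6-17), the imputed gap is 2 (16-17), so two episodes become one.

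**Effect of bounding.** The start becomes the earlier of the imputed date and the known end. Among Placebo-country onsets after Dose 2 in a month without a dose, the share leaving the window changes as follows.

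| Event length | Unbounded | Bounded |
|---|---|---|
| 3 days | 24.1% | 6.2% |
| 5 days | 24.1% | 600/5,219 = 11.5% |
| 10 days | 24.1% | 20.7% |

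This 11.5% has a different base from the one above. As a share of all in-window onsets after Dose 2, 5-day events go from 11.5% to 600/10,950 = 5.5%. Every event in this setting whose recorded end is on or before Day 30 is kept. Those still lost end after Day 30, so their recorded end does not settle the matter.

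**The case against.** The best case against is that the effect is small and balanced. The exceptions govern most AE starts near a dose, and at nominal dosing the window loss is confined to one dose in one type of country. The error runs in both directions. The comparator is chosen by country and no Placebo-country arm has a Visit 5 injection, so the rule acts alike in all three arms. Negative durations reach listings only, since solicited-event durations are summed from daily records. All of this stands, and it limits the size of the effect. It does not justify dates that contradict the record.

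Some stronger readings are tempting but unsupported:

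- A reader might take 24% as the general loss of in-window events. It applies only when the start day is missing, the dose is Dose 2, the country uses Placebo and the onset month holds no dose.
- A reader might say each lost event costs 2 percentage points in a group of 50 (1/50). The endpoint counts subjects with at least one event, so for any unsolicited AE this is true only if the lost event was the subject's sole qualifying one.
- A reader might infer that RTI counts are inflated. Merging is as possible as splitting, and section 9.2 does not show that RTI dates are ever partial. Nor can days between an imputed end and a later recorded onset simply be counted as symptom-free: the onset day itself had symptoms.
- A reader might prefer month-end or 31 December for missing end dates. That creates new errors. An RTI of 3-8 January with the end day missing, followed by a new one on 5 February, has 20 symptom-free days under the present rule (16 January to 4 February) but only 4 under month-end (1-4 February), a false merge. An AE of 3-6 March, truly 4 days, would last 29 days instead of 13.

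**Conclusion.** The point holds in limited form. Followed as written, section 10.1.2.1 can give a start after the known end or an end before the known start, and can place outside the primary window an AE whose recorded end proves onset within it. The impossible orderings can occur in any country. The window loss arises mainly after Dose 2 in Placebo countries, at about 11.5% of in-window AEs with a missing start day. That figure assumes nominal dosing, evenly spread onsets, dose dates spread over the year, a correct before/after flag, and that the Visit 5 injection counts as a study dose.

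The SAP does not say how common partial dates are, so the effect on any reported percentage is unknown, and nothing shows a bias between arms. The RTI effect is conditional on partial symptom dates and on reading the general rule as covering them.

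**What to change.** Keep the 15th and 30 June defaults and the AE-start exceptions, and add to section 10.1.2.1:

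> An imputed start date is set to the earlier of the imputed date and the event's known end date; an imputed end date is set to the later of the imputed date and the event's known start date; the same bounds apply to RTI symptom dates.

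Do not move to month-end or 31 December for end dates.

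The cost is one sentence and a minimum/maximum in the date derivation, best made before the statistician is unblinded at the Day 61 analysis. The limits should be understood. The bounds remove all impossible orderings. They leave some window misclassification where the event ends after Day 30, and late events moved in. They do not correct an RTI split or merge where the imputed date is already consistent with the recorded one: in the December split above, a known start of 12 December leaves the imputed end at 15 December.

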3.2. Endpoints

3.2.1. Primary endpoints

- Occurrence of adverse events (AEs) from first vaccination (Day 1) up to Day 61
 - Occurrence of each solicited local and general AE, during a 7-day follow-up period after each vaccination (i.e., the day of vaccination and 6 subsequent days)
 - Occurrence of any unsolicited AE, during a 30-day follow-up period after each vaccination (i.e., the day of vaccination and 29 subsequent days)
 - Occurrence of any serious adverse event (SAE) from Day 1 up to Day 61
 - Occurrence of episode of spontaneous or excessive bleeding (AE of special interest), during a 30-day follow-up period after each vaccination

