2010	Protocol violation (inclusion/exclusion criteria including age)	All	Immunogenicity
2040	Administration of any medication forbidden by the protocol: 
Any investigational or non-registered product (drug) other than the study vaccines used during the study periodLong-acting immune-modifying drugs administered at any time during the study periodImmunosuppressants or other immune-modifying drugs administered chronically (i.e., more than 14 days in total) during the study periodImmunoglobulins and/or any blood products administered during the study period	Visit 3, 5, 7	Immunogenicity
2050	Underlying medical condition forbidden by the protocol	Visit 3, 5, 7	Immunogenicity
2060	Intercurrent medical condition → Intercurrent medical condition that has the capability of altering immune response, or alteration of initial immune status (suspected or confirmed immunosuppressive or immunodeficient condition) which may influence immune response	Visit 3, 5, 7	Immunogenicity
2070	Concomitant infection not related to the vaccine which may influence immune response	Visit 3, 5, 7	Immunogenicity
2080	Subjects did not comply with vaccination schedule:- Number of days between dose 1 and dose 2 is outside [23-44 days]	Visit 3	Immunogenicity

Code	Condition under which the code is used	Visit (timepoints) where the code is applicable	Applicable for analysis set
2090	Subjects did not comply with blood sample schedule 
 Number of days between dose 1 and visit 3 blood sample is outside [23-44 days] Number of days between dose 1 and visit 5 blood sample is outside [60-81 days] Number of days between dose 2 and visit 5 blood sample is outside [28-37 days] for RSV 2D group Number of days between visit 5 blood sample and visit 7 blood sample is outside [92-148 days] 	Visit 3, 5, 7	Immunogenicity
2100	Serological results not available post-vaccination:- No immunological result at visit x for all 2 tests - RSV A Neutralising antibody titer and RSVPreF3-specific IgG antibody concentration	Visit 3, 5 and 7	Immunogenicity

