10.1.3.10. Onset day

The onset day for an event (e.g. AE, medication, vaccination) is the number of days between the last study vaccination and the start date of the event. This is 1 for an event occurring on the same day as a vaccination (and reported as starting after vaccination).

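### Imputing a missing AE start day to the day before a later dose always puts the event outside the 30-day window when doses are more than 30 days apart, even if most possible dates are inside

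*SAP*

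**What the plan says.** The default in SAP 10.1.2.1 is "A missing day will be replaced by 15". Adverse event start dates are an exception when the month contains a study dose. An event flagged as after vaccination takes the date of the first or only dose of that month. For an event flagged as before vaccination, "the imputed date will be one day before the first (or only) study dose given during that month". When day and month are both missing, the same rule applies at the level of the year.

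Four other rules decide where the imputed date lands:

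- Attribution (10.1.1): "The dose relative to an event is the most recent study dose given to a subject prior to the start of a given event".
- Day count (10.1.3.10), on the onset day: "This is 1 for an event occurring on the same day as a vaccination".
- Selection of unsolicited events (5.3.2.4): "assignment to time intervals will be done by day of onset and not by days ongoing/persisting".
- Primary endpoint (3.2.1): "Occurrence of any unsolicited AE, during a 30-day follow-up period after each vaccination (i.e., the day of vaccination and 29 subsequent days"). The bleeding events of special interest also have a 30-day window after each vaccination.

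On spacing, code 2080 in 4.2.3.1 eliminates a subject from the per-protocol set if "Number of days between dose 1 and dose 2 is outside [23-44 days"]. Table 4 allows 28 to 37 days from Visit 3 to Visit 5 and 60 to 81 days from Visit 1 to Visit 5.

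**The concern.** The two branches of the rule lean in opposite directions. The after-vaccination branch picks the dose date, which is Day 1, so the event is counted. The before-vaccination branch, when the dose in question is a later one, picks the last date the event could have started. That is the date least likely to lie in the window of the preceding dose.

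Whether such an event counts towards a primary safety endpoint is then settled by how many days separate two visits, and not by when the event could have begun. A one-day shift of the later visit, from 30 to 31 days, changes the answer. Section 5.3.2.3 takes care to avoid a downward bias in the denominators for solicited events; this rule brings one in for unsolicited events.

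**Working it through.** **Set-up.** Let d be the number of days from the preceding dose to the later dose, and m the day of the month of the later dose. The preceding dose is in an earlier month, so the later dose is the first or only one in its month. The preceding dose is on Day 1 (10.1.3.10), so the later dose is on Day d + 1.

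**Imputed onset.** One day before Day d + 1 is Day d. The window is Days 1 to 30 (3.2.1).

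- d = 30 (nominal: Day 1 to Day 31, Day 31 to Day 61): Day 30, inside.
- d = 31: Day 31, outside.
- d = 44: Day 44, outside.

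Example: Dose 1 on 10 September 2019, window to 9 October. Dose 2 on 10 October gives an imputed onset of 9 October, Day 30, counted. Dose 2 on 11 October gives 10 October, Day 31, not counted.

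**Dates the event could have had.** The recorded month and the flag allow the 1st to day m − 1, which is m − 1 dates running from Day d + 2 − m to Day d. For d above 30, the number inside the window is 30 − (d + 2 − m) + 1 = m − d + 29, when this is positive. At least one date is inside only if m ≥ d − 28.

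| d | m | Possible days | Dates in window | Rule assigns |
|---|---|---|---|---|
| 31 | 20 | 13 to 31 | 18 of 19 | Day 31, out |
| 35 | 20 | 17 to 35 | 14 of 19 | Day 35, out |
| 35 | 5 | 32 to 35 | 0 of 4 | Day 35, out (correct) |

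**How often the recorded month reaches into the window.** Taking every preceding-dose date over four calendar years as equally likely, m ≥ d − 28 holds for 93% of calendar positions at d = 31, 80% at d = 35, 74% at d = 37 and 51% at d = 44. Imputing the earliest consistent date would keep the event in the window in these shares. The current rule keeps it in 0% at every d above 30.

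**Can intervals above 30 days occur?** Of the 22 Dose 1 to Dose 2 intervals from 23 to 44 days, 14 exceed 30. Of the 10 Visit 3 to Visit 5 intervals from 28 to 37 days, 7 do. Of the 220 pairs, 45 sum to less than 60 days and none to more than 81, which leaves 175. Of these, 174 have at least one interval above 30; the exception is 30 + 30. These are counts of allowed values, not frequencies.

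**Two doses in one month.** This is possible only for d ≤ 30. Enumerating 365 Dose 1 dates gives 24.4% (89/365) at d = 23, 7.9% (29/365) at d = 28 and 1.9% (7/365) at d = 30. If the flag then means before Dose 2, an event after Dose 1 is imputed to before Dose 1 and falls under 5.3.2.4: "Only vaccine-emergent adverse events will be analyzed, i.e., excluding those after a subject has given informed consent but before vaccination". If the flag refers to the first dose of that month, nothing is lost.

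**The case against.** A reader might infer that the rule wrongly drops every such event once the interval exceeds 30 days. The arithmetic does not support that. When m < d − 28, no possible date is in the window and exclusion is right: about 20% of calendar positions at d = 35 and 49% at d = 44. On the nominal schedule the rule keeps the event.

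A reader might also infer that events between two doses in the same month are certainly lost. Section 10.1.2.1 does not say which dose the flag refers to in that case, and its anchor on the first or only dose can be read as the first dose of that month. Section 10.1.1 does apply the flag to any study dose, but only for events starting on a dose day. So this is an ambiguity to close, not a demonstrated loss. The 24.4% share belongs to the shortest allowed interval, and all three shares assume Dose 1 dates spread evenly over the year, whereas Dose 1 is given before the RSV season.

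Table 4 and code 2080 define the per-protocol set for immunogenicity, while safety is analysed on the Exposed Set. That is correct. The Exposed Set does not exclude longer intervals, but the SAP gives no distribution of them.

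No bias between groups is shown. The rule uses no group information, all arms are injected at Visits 1 and 3, and at Visit 5 either all arms within a country are injected or, with Placebo, none. SAEs are also tabulated to Day 61 and to the season ends, later unsolicited events remain in a listing, and a subject percentage changes only if the moved event was that subject's only qualifying one.

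Finally, any imputation is partly arbitrary, and the earliest date can over-count. That is a real cost. But with doses more than 30 days apart, the present rule cannot place a late event in the window; it can only remove an event that belonged there.

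**Conclusion.** The point stands as a minor one. For an event with a missing start day, flagged before a later dose that is the first or only dose of its month, the SAP's own rules give an imputed onset of Day d. With d above 30, the event always falls outside the 30-day unsolicited-AE and bleeding windows. The result is wrong only if the true onset was in the window, which requires m ≥ d − 28. Nothing else in the SAP corrects it, and the direction is under-counting.

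The size cannot be stated. It depends on how many events have a missing start day, how many of those carry the flag in a month with a later dose, and how often intervals exceed 30 days in the Exposed Set. The SAP gives none of these, and the effect may be zero. The conclusion assumes that formulation buffer counts as a study dose. The Visit 5 part does not apply in Placebo countries, where nothing is injected at that visit.

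**What to change.** Amend 10.1.2.1 in two sentences, for the missing-day rule and for the missing day-and-month rule:

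1. For an event flagged before a dose other than Dose 1, impute the earliest date consistent with the recorded month or year, but not before the preceding study dose.
2. State which dose the flag refers to when two doses fall in the same month or year, so that an event after Dose 1 is never imputed to before Dose 1.

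If the later dose was on the 1st, no date in the recorded month precedes it; such a record should be queried.

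The cost is a small change to the derivation code. The downside is that a few events that truly began after Day 30 may be counted in the window, which is the cautious direction for a primary safety endpoint.
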